1.6. Compliance Statement

This study will be conducted in full accordance with the International Conference on Harmonisation (ICH) Good Clinical Practice (GCP) Consolidated Guideline (E6) and any applicable national and local laws and regulations (e.g., Title 21 Code of Federal Regulations [21CFR] Parts 11, 50, 54, 56, 312, and 314, European Union [EU] Directive 20/EC and 28/EC). Any episode of noncompliance will be documented.

The investigator is responsible for performing the study in accordance with this protocol and the applicable GCP guidelines referenced above for collecting, recording, and reporting the data accurately and properly. Agreement of each investigator to conduct and administer this study in accordance with the protocol will be documented in separate study agreements with the sponsor and other forms as required by national authorities.

Each investigator is responsible for ensuring the privacy, health, and welfare of the patients during and after the study and must ensure that trained personnel are immediately available in the event of a medical emergency. Each investigator and the applicable study staff must be familiar with the background to, and requirements of, the study and with the properties of the study drug(s) as described in the Investigator's Brochure or prescribing information.

The principal investigator at each investigational center has the overall responsibility for the conduct and administration of the study at that center and for contacts with study management, with the Independent Ethics Committee/Institutional Review Board (IEC/IRB), and with local authorities.

1.7. Population To Be Studied

Based on the anticipated mode of action (MoA) of laquinimod in HD, an intervention to reduce CNS inflammation as early as possible would be desirable to prevent further neuronal dysfunction and death. However, the rate of progression in signs and symptoms makes it difficult to detect slowing of disease in a feasible way in terms of treatment length in patients without signs of disease. Therefore, patients with clinical symptoms that are measurable, but with a retained functional capacity will be selected. Further, concomitant medications with antipsychotic drugs may confound the data due to side effects in the motor and cognitive domain, and thus these drugs will be disallowed in the study. It is also known that cytosine-adenosine-guanine (CAG) repeat length in the mutant huntingtin gene influence disease progression and course. To reduce variability in the study, patients will be selected from a pre-defined range of CAG repeat lengths frequently observed in the clinic.

Thus, the target patient population will be adult patients, with a CAG repeat length between 36 and 49, and the basic eligibility criteria will select a patient population with symptoms of HD, as assessed by a Unified Huntington's Disease Rating Scale Total Motor Score (UHDRS-TMS) >5 , but with a largely retained functional capacity, as assessed with a HDRS-Total Functional Capacity (UHDRS-TFC) score ≥ 8 . This will recruit a symptomatic early HD patient population.

The criteria for study eligibility are described in Section 4.1 and Section 4.2, respectively.

1.8. Relevant Literature and Data

Relevant literature is cited above. Further literature and data may be found in the current Investigator's Brochure.

2. PURPOSE OF THE STUDY AND STUDY OBJECTIVES

2.1. Purpose of the Study

The purpose of this Phase II clinical study is to investigate the efficacy and safety of multiple doses of laquinimod (0.5, 1.0 and 1.5 mg/day) as a potential treatment for patients with Huntington's disease (HD).

As no drug is currently available to treat HD disease progression, the study will be placebo controlled.

Prior to 10 January 2016, a total of 400 patients were planned to be equally randomized in a 1:1:1:1 ratio (100 patients within each treatment arm) to receive laquinimod 0.5, 1.0, 1.5 mg/day, or matching placebo for 52 weeks.

As of 10 January 2016, following the decision to discontinue treatment of the laquinimod 1.5 mg dose arm, additional eligible patients who are enrolled will be randomized in a 1:1:1 ratio to receive laquinimod 0.5 mg/day, 1.0 mg/day, or matching placebo for 52 weeks. Approximately 300 patients (100 patients within each study arm), plus the 30 patients who were already randomized to the laquinimod 1.5 mg treatment arm, are planned to be enrolled in the study.

This is the first clinical study with laquinimod in HD. Therefore, no clinical data on the effects of laquinimod in patients with Huntington's disease is available, and a wide dose range exploration is warranted.

Clinical data from patients with relapsing remitting multiple sclerosis (RRMS) show a benefit of laquinimod treatment of 0.6 mg/day on brain atrophy and disability progression after 1 year of treatment, also in patients without relapses during this period. A disproportionately large effect on disability compared to relapses was also observed. The results suggest that in addition to peripheral inflammatory modulating effects, laquinimod could also have neuroprotective effects, and a mode of affecting central nervous system (CNS) inflammatory processes beyond the classical MS dogma of active T-cell driven lesions. This is important in Huntington's disease where intrinsic CNS inflammatory phenotypes are observed to correlate with disease progression.

The study aims to detect potential beneficial effects in deteriorating clinical signs and symptoms of HD. Based on previous studies in patients with HD, the UHDRS-TMS has been shown to be one of the more sensitive clinical measures to detect decline in symptoms of HD, and hence TMS has been chosen as primary endpoint.

2.2. Study Objectives

2.2.1. Primary Study Objective

The primary objective of this study is to assess the efficacy of laquinimod 0.5 and 1.0 mg qd in patients with HD after 12 months of treatment using the Unified Huntington's Disease Rating Scale (UHDRS) Total Motor Score (TMS).

Due to the decision from 10 January 2016 to discontinue treatment of the laquinimod 1.5 mg dose arm, and the low number of enrolled patients compared to the target at this time, data from

the laquinimod 1.5 mg treatment arm will be presented descriptively only, and will not be included in any inferential analyses for efficacy or safety.

2.2.2. Secondary Study Objectives:

- To assess the effect of laquinimod on brain atrophy in patients with HD after 12 months of treatment using MRI measures of caudate volume.
- To assess the effect of laquinimod on the cognitive capacity in patients with HD after 12 months of treatment using the cognitive assessment battery (CAB) for patients with HD [comprised of: Symbol Digit Modalities Test (SDMT), Emotion Recognition, Trail Making Test, Hopkins Verbal Learning Test, revised (HVLT-R), Paced Tapping at 3 Hz, One Touch Stockings of Cambridge (OTS, abbreviated 10 trial version)].
- To assess the effect of laquinimod on the clinical global impression in patients with HD after 12 months of treatment using the Clinician's Interview-Based Impression of Change plus Caregiver Input (CIBIC-Plus)
- To assess the effect of laquinimod on the functional capacity in patients with HD after 12 months of treatment using the UHDRS-TFC scale

2.2.3. Exploratory Study Objectives:

- To assess the effect of laquinimod on brain atrophy in patients with HD after 12 months of treatment using MRI measures of whole brain volume, white-matter volume and ventricular volume.
- To assess the effect of laquinimod on the functional capacity in patients with HD after 12 months of treatment using the UHDRS-functional assessment (FA) scale
- To assess the effect of laquinimod on motor function in patients with HD after 12 months of treatment using the objective instrument Q-Motor
- To assess the effect of laquinimod on physical performance in patients with HD after 12 months of treatment using the modified Physical Performance Test (mPPT).
- To assess the effect of laquinimod on the quality of life in patients with HD after 12 months of treatment using the Huntington's Disease Quality of Life (HD-QoL) and EQ-5D-5L instruments
- To assess the effect of laquinimod on work productivity in patients with HD after 12 months of treatment.
- To assess the effect of laquinimod on functional impairment due to cognitive decline in patients with HD after 12 months of treatment using the Clinical Dementia Rating - Sum of Boxes (CDR-SB)
- To assess the effect of laquinimod on depression and anxiety in patients with HD after 12 months of treatment using the Hospital Anxiety and Depression Scale (HADS)
- To assess the effect of laquinimod on behavioral signs and symptoms in patients with HD after 12 months of treatment using the Problem Behaviors Assessment-Short form (PBA-s)
- To evaluate the pharmacokinetics of laquinimod and its metabolites in patients with HD

- To investigate the relationship between exposure to laquinimod and its metabolites and outcome measures (eg, clinical effect and toxicity parameters).

2.2.4. Safety and Tolerability Study Objectives:

- To evaluate safety and tolerability of laquinimod in patients with HD during 12 months of treatment by evaluating adverse events (AEs), electrocardiography (ECG), and clinical laboratory parameters, vital signs, physical examinations, and premature discontinuations from the study.

2.2.5. Ancillary Study Objectives:

- To explore potential correlation between genetic polymorphisms in deoxyribonucleic acid (DNA) and pharmacokinetics, clinical response to laquinimod, and/or adverse drug reactions, if these occur
- To explore potential correlation between ribonucleic acid (RNA) expression profile in blood cells and clinical response to laquinimod
- To evaluate changes in cytokines and other soluble protein levels following treatment with laquinimod as potential biomarkers for laquinimod mechanism of action and/or response predictive factors
- To explore gene expression and/or protein profile in monocytes in response to laquinimod treatment
- To explore change in microglial activation state in response to treatment with laquinimod
- To assess the correlation between microglial activation state at baseline and the clinical characteristics of HD patients (age, gender, number of triplets, disease onset, disease duration, motor and behavioral scores).
- To explore changes in MRS metabolite levels in response to treatment with laquinimod that reflect neuronal integrity (NAA) and astrocytosis (myo-inositol) in the putamen and frontal white matter.

3. STUDY DESIGN

3.1. General Design and Study Schema

This is a multicenter, randomized, double-blind, placebo-controlled, parallel-group study to evaluate the efficacy and safety of laquinimod treatment at dosages of 0.5, 1.0, and 1.5 mg/day in adults with Huntington's Disease.

The study will consist of a screening period (2 weeks up to 5 weeks), followed by a 52-week double-blind treatment period and a follow-up visit (one month after end of treatment). Prior to 10 January 2016, a total of 400 patients were planned to be equally randomized in a 1:1:1:1 ratio (100 patients within each treatment arm) to receive laquinimod 0.5, 1.0, 1.5 mg/day, or matching placebo for 52 weeks. A total of 123 patients were randomized prior to 10 January 2016.

As of 10 January 2016, following the decision to discontinue treatment of the laquinimod 1.5 mg dose arm, additional eligible patients who are enrolled will be randomized in a 1:1:1 ratio to receive laquinimod 0.5 mg/day, 1.0 mg/day, or matching placebo for 52 weeks. Approximately 300 patients (100 patients within each study arm), plus the 30 patients who were already randomized to the laquinimod 1.5 mg treatment arm, are planned to be enrolled in the study.

After signing the informed consent, including consent to provide a blood sample for genetic analyses including CAG repeat length analysis, patients will be screened for a period of 2 weeks up to 5 weeks in order to determine whether they are eligible to participate in the study. Patients with a legal guardian should be consented according to local requirements.

The procedures and assessments performed during each of the study visits are detailed in Section 3.11.

During the visits, vital sign measurements, physical examinations and ECG should preferably be performed prior to the blood draw for clinical laboratory tests and pharmacokinetic sampling. Further, the efficacy assessments (TMS, HD-CAB, CIBIC-plus and TFC) should be done prior to the exploratory assessments.

Patients who complete all scheduled visits will have final procedures and assessments performed at the final visit (Visit 8, Month 12). Patients who withdraw from the study before completing the 52-week evaluation period will have Visit 8 procedures and assessments performed at their last visit.

An independent DSMB will oversee the study. The DSMB will review unblinded accumulating safety data on a regular basis to ensure the continuing safety of the study patients and study conduct issues.

The study schema is presented in [Figure 1](#) (prior to 10 January 2016) and in [Figure 2](#) (from 10 January 2016).

Figure 1: Overall Study Schema (prior to 10 January 2016)

[figure not shown]
[figure not shown]

Figure 2: Overall Study Schema (from 10 January 2016)

3.2. Primary, Secondary and Exploratory Measures and Endpoints

3.2.1. Primary Efficacy Measure and Endpoints

The primary efficacy variable and endpoint for this study is the change from baseline in the UHDRS-TMS (defined as the sum of the scores of all UHDRS-TMS subitems) at Month 12/ ET (evaluated at baseline and Months 1, 3, 6 and 12).

3.2.2. Secondary Efficacy Measures and Endpoints

The secondary efficacy variables and endpoints for this study are:

- Percent change from baseline in caudate volume at Month 12/ET (evaluated at baseline and Month 12)
- Change from baseline in HD-CAB total score (sum of the standardized sub-components) at Month 12/ET (evaluated at baseline and Months 6 and 12)
- CIBIC-Plus global score at Month 12/ET (evaluated at Months 6 and 12) as compared to baseline (rated by an independent rater)
- Change from baseline in UHDRS- TFC at Month 12/ET (evaluated at baseline and Months 6 and 12)

3.2.3. Exploratory Efficacy Measures and Endpoints

The exploratory efficacy variables and endpoints for this study are:

- Change from baseline in brain atrophy as defined by the percentage change in volume in: whole brain volume and white-matter volume at Month 12/ET and absolute change in ventricular volume at Month 12/ET (evaluated at baseline and Month 12)
- Change from baseline in UHDRS- FA at Month 12/ET (evaluated at baseline and Months 6 and 12)
- Change from baseline in Q-Motor assessments at Month 12/ET (evaluated at baseline and Months 1, 3, 6 and 12)
- Change from baseline in mPPT at Month 12/ET (evaluated at baseline and Months 6, and 12)
- Change from baseline in HD QoL and EQ-5D-5L at Month 12/ET (evaluated at baseline and Month 12)
- Change from baseline in WLQ at Month 12/ET (evaluated at baseline and Month 12)
- Change from baseline in HD-CAB sub-components at Month 12/ET (evaluated at baseline and Months 6 and 12):
Symbol Digit Modalities Test (SDMT), Emotion Recognition, Trail Making Test, Hopkins Verbal Learning Test, revised (HVLTR), Paced Tapping at 3 Hz, One Touch Stockings of Cambridge (OTS, abbreviated 10 trial version)
- Change from baseline in CDR-SB at Month 12/ET (evaluated at baseline and Month12)
- Change from baseline in HADS at Month 12/ET (evaluated at baseline and Month 12)
- Change from baseline in PBA-s at Month 12/ET (evaluated at baseline and Month 12)

3.2.4. Safety Measures and Endpoints

The safety of laquinimod will be assessed throughout the study by evaluating adverse events, clinical laboratory test results, vital signs measurements, electrocardiography (ECG), physical examination results, and suicidality (as assessed by changes from baseline in C-SSRS scores).

3.2.5. Tolerability Measures and Endpoints

Tolerability variables and endpoints will include the following:

- Proportion of subjects (%) who prematurely discontinued from the study, reason of discontinuation and the time to ET
- Proportion of subjects (%) who prematurely discontinued from the study due to AEs and the time to ET

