3.6.2. Early Termination (ET)

An ET visit should be completed for all patients who prematurely terminate treatment or who become pregnant (see Section 3.11.4 for details of procedures).

Early termination refers to the study drug termination and not termination of the patient from the study. Patients will be asked to continue all scheduled visits and safety assessments after study drug discontinuation (with the exception of drug dispensing and accountability, pregnancy testing, and pharmacokinetic sampling).

Patients in the 1.5 mg/day (high dose) treatment arm, whose treatment with laquinimod was discontinued, were invited to attend an early termination visit (to return study medication and perform drug accountability). At this visit, only safety assessments were to be completed. These included vital signs, clinical laboratory tests, pregnancy test, adverse event inquiry, drug accountability, review of concomitant medication, and C-SSRS (see also Section 3.11.3.1.5). Patients were asked to continue scheduled follow up safety visits per the current schedule.

Women of child bearing potential should continue using 2 acceptable contraception methods up to 30 days after the last dose of study medication has been administered.

Moderate/strong CYP3A4 inhibitors are disallowed during the 30 days after the last laquinimod dose has been administered (see [Appendix B](#)).

Plasma levels of drugs that are CYP1A2 substrates may decrease when combined with laquinimod and within 30 days after the last laquinimod dose, rendering these drugs less effective (see [Appendix C](#)).

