4.3. Withdrawal Criteria and Procedures

In accordance with the Declaration of Helsinki (in accordance with the applicable country's acceptance), each patient is free to withdraw from the study at any time. The investigator also has the right to withdraw a patient from the study in the event of intercurrent illness, adverse events, pregnancy (see Section 7.3.3), or other reasons concerning the health or well-being of the patient, or in the event of lack of cooperation. In addition, a patient may be withdrawn from the study as described in Sections 3.6, 3.8, 3.11.4, 5.4, and 7.1.7.

Specific safety reasons for withdrawing a patient from the study are described in detail in [Appendix A](#) and Section 3.6. These include:

- Elevated liver enzymes (as detailed in [Appendix A](#))
- Pregnancy

- Need for concomitant treatment with moderate and strong CYP3A4 inhibitors
- Patients that are diagnosed with a malignant solid or liquid tumor
- Acute coronary syndrome, myocardial infarction or any major cardiovascular event

Should a patient decide to withdraw after administration of study drug(s), or should the investigator decide to withdraw the patient, all efforts will be made to complete and report all observations up to the time of withdrawal. A complete final evaluation at the time of the patient's withdrawal (including all Visit 8 procedures) should be made and an explanation given as to why the patient is withdrawing or being withdrawn from the study.

The reason for and date of withdrawal from the study must be recorded on the source documentation and transcribed onto the CRF. If a patient withdraws consent, every attempt will be made to determine the reason. If the reason for withdrawal is an adverse event or a clinically significant abnormal laboratory test result, monitoring will be continued at the discretion of the investigator (e.g., until the event has resolved or stabilized, until the patient is referred to the care of a health care professional, or until a determination of a cause unrelated to the study drug or study procedure is made). The specific event or test result(s) must be recorded on the source documentation and transcribed onto the CRF.

All evaluations should be performed according to the protocol on the last day the patient takes study drug, or as soon as possible thereafter. If it is not possible to schedule the ET visit within 2 weeks after end of treatment, only the safety evaluations for that visit need to be performed.

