7.1.2. Recording and Reporting Adverse Events

For adverse event recording, the study period is defined for each patient as that time period from signature of the informed consent form through the end of the follow-up period. For this study, the follow-up period is defined as 1 month following the last dose of study medication

All adverse events that occur during the defined study period must be recorded on the source documentation and transcribed onto the CRF, regardless of the severity of the event or judged relationship to the study drug. For serious adverse events, the Serious Adverse Event Form must also be completed and the serious adverse event must be reported immediately (see Section 7.1.5.3.1).

At each contact with the patient, the investigator or designee must query the patient for adverse events by asking an open-ended question such as, "Have you had any unusual symptoms or medical problems since the last visit? If yes, please describe." All reported or observed signs and

symptoms will be recorded individually, except when considered manifestations of a medical condition or disease state. A precise diagnosis will be recorded whenever possible. When such a diagnosis is made, all related signs, symptoms, and any test findings will be recorded collectively as a single diagnosis on the CRF and, if it is a serious adverse event, on the Serious Adverse Event Form.

The clinical course of each adverse event will be monitored at suitable intervals until resolved or stabilized or returned to baseline, or until the patient is referred to the care of a health care professional, or until a determination of a cause unrelated to the study drug or study procedure is made.

The onset and end dates, duration (in case of adverse event duration of less than 24 hours), action taken regarding study drug, treatment administered, and outcome for each adverse event must be recorded on the source documentation and transcribed onto the CRF.

The relationship of each adverse event to study drug treatment and study procedures, and the severity and seriousness of each adverse event, as judged by the investigator, must be recorded as described below.

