Plasma levels of drugs that are CYP1A2 substrates may decrease when combined with laquinimod and within 30 days after the last laquinimod dose, rendering these drugs less effective.

In general, it is recommended to avoid the use of CYP1A2 substrates in clinical trials of laquinimod. Therapeutic alternatives may be considered in context.

For additional information on concomitant use of laquinimod with CYP1A2 substrates, please refer to Section 5.3.2.

5. Management of Pregnancy and Pregnancy Testing During the Study

Exposure to laquinimod during pregnancy should be avoided.

Women of child-bearing potential (women who are not post menopausal or who have not undergone surgical sterilization) must practice an acceptable method of birth control for 30 days before taking the study treatment, and 2 acceptable methods of birth control during all study duration and until 30 days after the last dose of treatment was administered.

Acceptable methods of birth control in this study include: Intrauterine device, barrier method (condom or diaphragm with spermicide) and hormonal methods of birth control (e.g. oral contraceptive, contraceptive patch, long-acting injectable contraceptive).

The patients' understanding of the importance of preventive pregnancy measures and their ability to follow the required instructions will be ascertained by the investigator and recorded in source documents at every visit. Any female patient who becomes pregnant during the study will discontinue her participation in the study and will not perform the activities described for scheduled follow-up visits.

To further emphasize the importance of use of acceptable contraception and avoidance of pregnancy under laquinimod exposure, and to reduce as much as possible the exposure to laquinimod if a pregnancy occurs despite all recommended measures, the following measures will be taken:

1. Female subjects of child-bearing potential (women who are not post menopausal or who have not undergone surgical sterilization) will be reminded at each study visit about:
 - a. The importance of using acceptable contraception.
The importance of immediately stopping the study drug and informing the site in any case of suspected pregnancy (following a positive urine test, absence of menstruation or any other reason suggesting pregnancy).

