 - additional investigations and follow-up per the investigator's discretion or sponsor's request

Necessary medical procedures including repeat labs will be performed based on clinical needs determined by the treating physician's judgement.

9. Guidance on monitoring subjects with CPK increase

- In case of CPK results $>ULN$, troponin and creatine kinase MB isoenzyme (CK-MB) will be tested by the central laboratory.
- In case of CPK $>10\times ULN$, an unscheduled visit to assess urine myoglobin will be required. The following blood tests will be repeated at the unscheduled visit: CPK, blood urea nitrogen, creatinine, electrolytes including potassium, calcium, phosphate.

10. Acute Coronary Syndrome, Myocardial Infarction or Any Major Cardiovascular Event

Patients who experience acute coronary syndrome, myocardial infarction or any major cardiovascular event will permanently discontinue treatment with study medication. Patients will be asked to continue all scheduled visits for safety assessment.

11. Liver Impairment

Patients who develop liver disease associated with liver functional impairment while participating in the study should stop study medication.

12. Renal Impairment

Patients who develop chronic renal disease associated with moderate-severe functional impairment, defined as estimated CrCl <60 mL/min/1.73 m², while participating in the study should stop study medication temporarily until normalization of renal function or confirmation of renal impairment diagnosis. In case moderate-severe renal impairment is diagnosed, the patient will permanently discontinue treatment with study medication.

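### Both tolerability endpoints count patients who leave the study but time them to stopping study drug, and the protocol does not settle whether a patient who stops drug and stays for visits is counted

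*Protocol*

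**What the plan says.** **Endpoints.** Section 3.2.5 gives two tolerability endpoints: the proportion "who prematurely discontinued from the study, reason of discontinuation and the time to ET", and the proportion "who prematurely discontinued from the study due to AEs and the time to ET". The Synopsis and Section 9.8.1 use the same wording.

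**Meaning of ET.** Section 3.6.2 states: "Early termination refers to the study drug termination and not termination of the patient from the study". Section 3.11.3.1.5 repeats this. Section 3.6.2 adds: "Patients will be asked to continue all scheduled visits and safety assessments after study drug discontinuation", apart from drug handling, pregnancy tests and PK samples.

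**AE window.** For AE recording, Section 7.1.2 says that "the follow-up period is defined as 1 month following the last dose of study medication".

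**Who leaves the study.** Section 4.3 introduces a list that includes pregnancy and major cardiovascular events with "Specific safety reasons for withdrawing a patient from the study are described in detail in" Appendix A and Section 3.6. Item 10 of Appendix A stops drug after a cardiovascular event and then says: "Patients will be asked to continue all scheduled visits for safety assessment". Item 5 of Appendix A says that a patient who becomes pregnant "will discontinue her participation in the study and will not perform the activities described for scheduled follow-up visits".

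**The concern.** Amendment 04 added Section 3.6.2 and so separated stopping drug from leaving the study. The tolerability endpoints were not changed to match. Their proportion refers to leaving the study and their time refers to stopping drug.

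These two proportions are the trial's tolerability result. A patient who stops drug because of an AE and continues to attend, as the protocol asks, is a tolerability failure in any ordinary sense. If sites differ in whether they code that patient as discontinued, the reported rate has no fixed meaning and the arms are hard to compare.

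The AE window raises a related question. Patients are asked to attend for safety after stopping drug, but the defined AE recording period may already have closed for them.

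**Working it through.** The protocol states no figure that can be recomputed here. The check sets its sections side by side.

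**1. Counted event against timed event.** The proportion in Sections 3.2.5 and 9.8.1 concerns leaving the study. ET in Sections 3.6.2 and 3.11.3.1.5 is the end of study drug, expressly not the end of participation. These are different events.

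**2. Status of a patient who is off drug and attending.** Section 3.6.2 keeps this patient in scheduled visits. Section 7.2 also refers to early-terminated patients who remain in the study for follow-up. Read literally, the patient has a time to ET but has not discontinued from the study.

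**3. Whether another summary fills the gap.** The objective in Section 2.2.4 (and in the Synopsis), the disposition summary in Section 9.5.1 and the AE summary in Section 9.8.2 are all worded in terms of leaving the study. No listed summary counts drug discontinuation as such.

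**4. Sections that point the other way.**
- Section 7.1.7: when treatment stops for an AE, the CRF termination page is completed then, and the event is described as a withdrawal.
- Section 3.11.4.1: completion requires compliance through the whole double-blind treatment, so an off-drug attender is not clearly a completer.
- Section 3.11.3.1.5: patients on 1.5 mg who stopped drug and kept attending are not completers (stated for that arm only).
- Section 4.3: the drug-stopping rules are called reasons to withdraw from the study, and the drug stop in the 1.5 mg arm is recorded as a sponsor-requested withdrawal.

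None of these says that ET counts as discontinuing from the study.

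**5. How the count depends on the reading.** Let d be the share of an arm that stops drug, s the share of those who stay for visits, and c the share of stayers coded as study discontinuations. The reported proportion is

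d × [1 − s × (1 − c)].

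The literal reading has c = 0 and gives d × (1 − s). If every drug stop is coded as a withdrawal, c = 1 and the result is d. As pure illustration, with values that are assumed and not taken from the protocol:

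- d = 10%, s = 75%: 10% × 0.25 = 2.5% if c = 0, and 10% if c = 1.
- d = 30%, s = 25%: 30% × 0.75 = 22.5% if c = 0, and 30% if c = 1.

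The protocol fixes none of d, s or c.

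**6. AE window.** Take a last dose at Month 2. Recording under Section 7.1.2 runs to 2 + 1 = Month 3. Scheduled visits run to Month 12, which leaves 12 − 3 = 9 months of visits after the defined window. For the same period:
- Section 7.1.6 states no time limit for 24-hour reporting of ischemic cardiac events, cerebrovascular events and deaths.
- Section 7.1.5.3.1 has SAEs after the defined period reported if the investigator learns of them.
- Section 7.1.2 asks for an AE query at every contact.

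The events left unclear are mainly the non-serious ones.

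**7. Who leaves the study.** For cardiovascular events, Section 4.3 lists withdrawal from the study, while Appendix A item 10 stops drug and continues visits. For pregnancy, Section 3.6.2 includes these patients under ET with its general request to continue visits, Section 7.2 speaks of stopping treatment, Section 7.3.6 of being withdrawn, and Appendix A item 5 of ending participation and scheduled follow-up visits.

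**The case against.** The strongest reply is that this is loose terminology and that drug stops will be captured in practice. Section 7.1.7 collects the AE-related stop on the termination page whether or not visits continue. Section 3.11.4.1 makes a completer of someone who finishes treatment. The appearance of ET inside the endpoint suggests that ET was the intended event. Most of this stands, and it means that an undercount cannot be asserted. It does not remove the defect. Section 7.1.7 covers only AE-related stops, the explicit non-completer rule covers only the 1.5 mg arm, and no section equates ET with leaving the study.

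A reader might also infer that cardiovascular events in off-drug patients would go unrecorded. Sections 7.1.6 and 7.1.5.3.1 do not support that.

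On pregnancy, the specific rule in Appendix A can fairly be read as overriding the general request in Section 3.6.2. That reduces the conflict, but Sections 7.2 and 7.3.6 still use different terms.

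Finally, definitions of disposition variables are often left to the SAP, which is not shown. Here, however, the protocol itself fixes both conflicting terms, including in its statistics section. An SAP could settle the derivation but could not change what sites were told to record.

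**Conclusion.** The concern holds as an inconsistency in definition. Both tolerability endpoints join a count of study discontinuation to a time to drug termination, and other sections give conflicting signals on how a patient who stops drug and stays should be coded.

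It is tempting to conclude that drug discontinuations are missed and the rates biased low. The documents do not show this. It follows only from the literal reading, which Section 7.1.7 in particular may override in practice. An undercount is possible and its size is unknown. The percentages above are illustrations and carry no evidential weight.

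The AE window is a secondary gap, mainly for non-serious AEs found at off-drug visits. The sections on cardiovascular events and pregnancy need reconciling. This review takes no position on which rule is right.

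These are descriptive summaries. The primary analysis, power and type I error are unaffected.

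**What to change.** 1. Define both tolerability endpoints as premature discontinuation of study drug, for all causes and due to AEs, with time to last dose. Report withdrawal from the study as a separate variable with its own reason and time.
2. Align the objective (Synopsis and Section 2.2.4), the endpoint lists (Synopsis, Sections 3.2.5 and 9.8.1), the disposition summary (Section 9.5.1) and the AE summary (Section 9.8.2) with these two variables.
3. State in Section 7.1.2 that AEs found at scheduled visits after drug discontinuation are recorded, and that they are summarised as off-treatment.
4. Reconcile Section 4.3 with Appendix A item 10 for cardiovascular events, and Sections 3.6.2, 7.2 and 7.3.6 with Appendix A item 5 for pregnancy, on whether the patient stops drug only or leaves the study.

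The cost is protocol wording and brief CRF completion guidance. The visits are already scheduled.
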